6.6.1.2. Adverse Events Leading to Treatment Discontinuation

The frequency (number and percentage) of patients with each of the following will be presented for TEAEs leading to permanent discontinuation of each study drug and study treatment, by treatment group:

- TEAEs leading to discontinuation of PF-05082566 by SOC and PT;
- Related TEAEs leading to discontinuation of PF-05082566 by SOC and PT;
- TEAEs leading to discontinuation of mogamulizumab by SOC and PT;
- Related TEAEs leading to discontinuation of mogamulizumab by SOC and PT;
- TEAEs leading to permanent discontinuation of study treatment;
- Related TEAEs leading to permanent discontinuation of study treatment.

The listing of all AEs leading to treatment discontinuation will also be provided with the relevant information.

6.6.2. Deaths

The frequency (number and percentage) of patients in the safety analysis set who died and who died within 30 days and within 60 days after last dose of study treatment as well as the cause of death, will be tabulated based on information from the 'Notice of Death' eCRFs, by treatment group.

- All deaths (within 30 days, and within 60 days);
- Deaths (within 30 days, and within 60 days) after last dose of study treatment;
- Cause of Death:
 - Disease under study;
 - Study treatment toxicity;
 - Unknown;
 - Other.

In addition, date and cause of death will be provided in individual patient data listing together with selected dosing information (study treatment received, date of first / last administration, dose) and will include the following information:

- AEs with fatal outcome (list preferred terms of AEs with outcome=Fatal, as well as AEs of Grade 5);
- Flag for death \leq 30 days and 31-60 days after last dose of study treatment.

6.6.3. Serious Adverse Events

The frequency (number and percentage) of patients with each of the following will be presented for treatment-emergent SAEs by treatment group:

- SAEs by SOC and PT;
- Related SAEs by SOC and PT.

The listings of all SAEs will also be provided with the relevant information with a flag for SAEs with onset outside of the on-treatment period.

6.6.4. Other Significant Adverse Events

The frequency (number and percentage) of patients with each of the following will be presented for irAEs, by treatment group:

- irAEs leading to death, by cluster and PT;
- Related irAEs leading to death, by cluster and PT;

- irAEs, by cluster and PT;
- irAEs, Grade ≥ 3 , by cluster and PT;
- Related irAEs, by cluster and PT;
- Related irAEs, Grade ≥ 3 , by cluster and PT;
- irAEs leading to permanent treatment discontinuation, by cluster and PT;
- Related irAEs leading to permanent treatment discontinuation, by cluster and PT;
- Serious irAEs, by cluster and PT;
- Related serious irAEs, by cluster and PT.

The listing of all irAEs will also be provided with the relevant information with a flag for irAEs with onset outside of the on-treatment period.

The frequency (number and percentage) of patients with each of the following will be presented for IRRs, by treatment group:

- IRRs leading to death, by PT;
- Related IRRs leading to death, by PT;
- IRRs, by PT;
- IRRs, Grade ≥ 3 , by PT;
- Related IRRs, by PT;
- Related IRRs, Grade ≥ 3 , by PT;
- IRRs leading to permanent treatment discontinuation, by PT;
- Related IRRs leading to permanent treatment discontinuation, by PT;
- Serious IRRs, by PT;
- Related serious IRRs, by PT;
- Time related to first onset of an IRR (infusion 1, infusion 2, infusion 3, infusion 4 or later).

The listing of all IRRs will also be provided with the relevant information with a flag for IRRs with onset outside of the on-treatment period.

6.6.5. Laboratory Data

6.6.5.1. Hematology and Chemistry Parameters

Laboratory results will be classified according to the NCI-CTCAE criteria version 4.03. Non-numerical qualifiers (with the exception of fasting flags) will not be taken into consideration in the derivation of CTCAE criteria (eg, hypokalemia Grade 1 and Grade 2 are only distinguished by a non-numerical qualifier and therefore Grade 2 will not be derived). Additional laboratory results that are not part of NCI-CTCAE will be presented according to the categories: below normal limit, within normal limits and above normal limit (according to the laboratory normal ranges).

Quantitative data will be summarized using simple descriptive statistics (mean, SD, median, Q1, Q3, minimum, and maximum) of actual values and changes from baseline for each nominal visit over time (unscheduled measurements would therefore not be included in these summaries as described in [Section 5.2.9](#)). End of Treatment visit laboratory results will be summarized separately. The changes computed will be the differences from baseline. Qualitative data based on reference ranges will be described according to the categories (ie, Low, Normal, High).

Abnormalities classified according to NCI-CTCAE toxicity grading version 4.03 will be described using the worst grade. For those parameters which are graded with two toxicities such as potassium (hypokalemia/hyperkalemia), the toxicities will be summarized separately. Low direction toxicity (eg, hypokalemia) grades at baseline and post baseline will be set to 0 when the variables are derived for summarizing high direction toxicity (eg, hyperkalemia), and vice versa.

For **WBC differential counts** (total neutrophil [including bands], lymphocyte, monocyte, eosinophil, and basophil counts), the absolute value will be used when reported. When only percentages are available (this is mainly important for neutrophils and lymphocytes, because the CTCAE grading is based on the absolute counts), the absolute value is derived as follows:

$$\text{Derived differential absolute count} = (\text{WBC count}) \times (\text{Differential \%value} / 100)$$

If the range for the differential absolute count is not available (only range for value in % is available) then Grade 1 will be attributed to as follows:

- Lymphocyte count decreased:
 - derived absolute count does not meet Grade 2-4 criteria, and
 - % value < % LLN value, and
 - derived absolute count $\geq 800/\text{mm}^3$.
- Neutrophil count decreased:
 - derived absolute count does not meet Grade 2-4 criteria, and

- % value < % LLN value, and
- derived absolute count $\geq 1500/\text{mm}^3$.

For **calcium**, CTCAE grading is based on Corrected Calcium and Ionized Calcium (C CALCIO). Corrected Calcium is calculated from Albumin and Calcium as follows:

Corrected calcium (mmol/L) = measured total Calcium (mmol/L) + 0.02 (40 - serum albumin [g/L])

Liver function tests: Alanine aminotransferase (ALT), aspartate aminotransferase (AST), and total bilirubin (TBILI) are used to assess possible drug induced liver toxicity. The ratios of test result over upper limit of normal (ULN) will be calculated and classified for these three parameters during the on-treatment period.

Summary of liver function tests will include the following categories. The number and percentage of patients with each of the following during the on-treatment period will be summarized by treatment group:

- ALT $\geq 3 \times \text{ULN}$, ALT $\geq 5 \times \text{ULN}$, ALT $\geq 10 \times \text{ULN}$, ALT $\geq 20 \times \text{ULN}$;
- AST $\geq 3 \times \text{ULN}$, AST $\geq 5 \times \text{ULN}$, AST $\geq 10 \times \text{ULN}$, AST $\geq 20 \times \text{ULN}$;
- (ALT or AST) $\geq 3 \times \text{ULN}$, (ALT or AST) $\geq 5 \times \text{ULN}$, (ALT or AST) $\geq 10 \times \text{ULN}$, (ALT or AST) $\geq 20 \times \text{ULN}$;
- TBILI $\geq 2 \times \text{ULN}$;
- Concurrent ALT $\geq 3 \times \text{ULN}$ and TBILI $\geq 2 \times \text{ULN}$;
- Concurrent AST $\geq 3 \times \text{ULN}$ and TBILI $\geq 2 \times \text{ULN}$;
- Concurrent (ALT or AST) $\geq 3 \times \text{ULN}$ and TBILI $\geq 2 \times \text{ULN}$;
- Concurrent (ALT or AST) $\geq 3 \times \text{ULN}$ and TBILI $\geq 2 \times \text{ULN}$ and ALP $> 2 \times \text{ULN}$;
- Concurrent (ALT or AST) $\geq 3 \times \text{ULN}$ and TBILI $\geq 2 \times \text{ULN}$ and (ALP $\leq 2 \times \text{ULN}$ or missing).

Concurrent measurements are those occurring on the same date.

Categories will be cumulative, ie, a patient with an elevation of AST $\geq 10 \times \text{ULN}$ will also appear in the categories $\geq 5 \times \text{ULN}$ and $\geq 3 \times \text{ULN}$. Liver function elevation and possible Hy's Law cases will be summarized using frequency counts and percentages.

An evaluation of Drug-Induced Serious Hepatotoxicity (eDISH) plot will also be created, with different symbols for different treatment groups, by graphically displaying.

- peak serum ALT(/ULN) vs peak total bilirubin (/ULN) including reference lines at ALT=3×ULN and total bilirubin =2×ULN.
- peak serum AST(/ULN) vs peak total bilirubin (/ULN) including reference lines at AST=3×ULN and total bilirubin =2×ULN.

In addition, a listing of all TBILI, ALT, AST and ALP values for patients with a post-baseline TBILI $\geq 2 \times$ ULN, ALT $\geq 3 \times$ ULN or AST $\geq 3 \times$ ULN will be provided.

Parameters with NCI-CTC grades available:

The laboratory toxicities will be tabulated using descriptive statistics (number of patients and percentages) during the on-treatment period. The denominator to calculate percentages for each laboratory parameter is the number of patients evaluable for CTCAE grading (ie, those patients for whom a Grade 0, 1, 2, 3 or 4 can be derived).

- The summary of laboratory parameters by CTCAE grade table will include number and percentage of patients with Grade 1, 2, 3, 4, Grade 3/4 and any grade(Grades 1-4), laboratory abnormalities during the on-treatment period.
- The shift table will summarize baseline CTCAE grade versus the worst on-treatment CTCAE grade. The highest CTCAE grade during the on-treatment period is considered as the worst grade for the summary.

The above analyses apply to hematology and chemistry evaluations which can be graded per CTCAE, ie:

- Hematology:

Hemoglobin (HB), Leukocytes (white blood cell decreased), Lymphocytes (lymphocyte count increased/decreased), Neutrophils / Absolute Neutrophils Count (ANC) (neutrophil count decreased), Platelet Count (PLT) (platelet count decreased), Coagulation (activated partial thromboplastin time (aPTT) and prothrombin time (INR)).

- Serum Chemistry:

Albumin (hypoalbuminemia), Alkaline Phosphatase (alkaline phosphatase increased), Alanine Aminotransferase (ALT) (ALT increased), Amylase (serum amylase increased), Aspartate Aminotransferase (AST) (AST increased), Total Bilirubin (blood bilirubin increased), Cholesterol (cholesterol high), Creatinine (creatinine increased), Creatine Kinase (CPK increased), Potassium (hypokalemia/ hyperkalemia), Sodium (hyponatremia/ hypernatremia), Magnesium (hypomagnesemia/hypermagnesemia), Calcium (hypocalcemia/ hypercalcemia), Glucose (hypoglycemia/hyperglycemia), Gamma Glutamyl Transferase (GGT) (GGT increased), Lipase (lipase increased), Phosphates (hypophosphatemia), Triglycerides (hypertriglyceridemia).

Parameters with NCI-CTC grades not available:

Hematology and chemistry evaluations which cannot be graded per CTCAE criteria will be summarized as frequency (number and percentage) of patients with:

- shifts from baseline normal to at least one result above normal during on-treatment period;
- shifts from baseline normal to at least one result below normal during on-treatment period.

In this study, these apply to the following parameters:

- Hematology: Absolute Monocytes, Absolute Eosinophils, Absolute Basophils;
- Serum Chemistry: Chloride, Total Urea, Uric Acid, Total Protein, C-Reactive Protein, Lactate Dehydrogenase (LDH).

6.6.5.2. Other Laboratory Parameters

All other parameters collected on the eCRF will be listed in dedicated listings presenting all corresponding collected information on the eCRF.

- Urinalysis: all urinalysis parameters (except for Proteinuria, which will be summarized with CTCAE grades);
- Other parameters: hormone, and immunology parameters;
- Pregnancy test.

The listings of laboratory results will be provided for all laboratory parameters. The listings will be sorted by parameters and assessment dates or visits for each patient. Laboratory values that are outside the normal range will also be flagged in the data listings, along with corresponding normal ranges. A listing of CTCAE grading will also be generated for those laboratory tests.

In addition, listings of abnormal values will be provided for hematology, chemistry, urinalysis, coagulation parameters. If there is at least one abnormal assessment for any parameter, all the data for that laboratory parameter will be included into the listing.

For all tests not mentioned above but present in the clinical data, a listing of patients with at least one result for the relevant test will be provided.

6.6.6. Vital Signs

Weight for the purposes of dose calculation will be recorded at screening and within 3 days pre-dose Day 1 of each cycle. Weight will not be collected at End of Treatment. Height will be measured at screening only.

Vital sign summaries will include all vital sign assessments from the on-treatment period. All vital sign assessments will be listed, and those collected outside the on-treatment period will be flagged in the listing.

All vital sign parameters will be summarized using descriptive statistics (mean, SD, median, Q1, Q3, minimum, and maximum) of actual values and changes from baseline for each visit over time. End of Treatment visit will be summarized separately. The changes computed will be the differences from baseline.

6.6.7. Electrocardiogram

ECG summaries will include all ECG assessments from screening and the on-treatment period. All ECG assessments will be listed, and those collected outside the on-treatment period will be flagged in the listing. QTcB and QTcF will be derived based on HR and QT (see below). The average of the replicate measurements should be determined after the derivation of the individual parameter at each time point.

Selecting Primary QT Correction for Heart Rate

The analysis of QT data is complicated by the fact that the QT interval is highly correlated with heart rate. Because of this correlation, formulas are routinely used to obtain a corrected value, denoted QTc, which is independent of heart rate. This QTc interval is intended to represent the QT interval at a standardized heart rate. Several correction formulas have been proposed in the literature. For this analysis we will use some of those methods of correction, as described below. The QT interval corrected for heart rate by the Bazett's formula, QTcB, is defined as

$$QTcB = \frac{QT}{\sqrt{RR}},$$

the QT interval corrected for heart rate by the Fridericia's formula, QTcF, is defined as:

$$QTcF = \frac{QT}{\sqrt[3]{RR}},$$

where RR represents the RR interval of the ECG, in seconds, and can be estimated as 60/Heart Rate.

Both formula produce similar results when the range of heart rates is not extreme. If QTcB and QTcF methods do not adequately correct QT for heart rate, an empirical correction specific to the study population can be derived.

These corrections were obtained by starting with the simple power model:

$$QT = a \times RR^b \quad (1)$$

and then used the natural log transformation to derive the equation:

$$\ln(QT) = \ln(a) + b \ln(RR) \quad (2)$$

The power model can be used to derive an empirical correction based on the reference group by fitting a linear mixed-effects regression model to the $\ln(QT)$ and $\ln(RR)$ data, estimating the slope b from Equation 2, and then applying that as a power in $QTcP(\text{msec}) = QT(\text{msec})/RR(\text{sec})^b$ to correct all the singlet data (on-drug as well as off-drug.)

Data will be summarized using $QTcF$ and $QTcB$. However, if these are not appropriate correction method for the data set, the results will also be summarized using $QTcP$.

ECG Summaries

The following analyses will be performed for each applicable ECG parameters (RR, PR, QRS, QT, ventricular rate -denoted as HR in what follows-, and QTc) by treatment group, during the on-treatment period. The denominator to calculate percentages for each category is the number of patients evaluable for the category.

- Pearson correlation between QT and HR, QTc (QTcB, QTcF and, if applicable, QTcP) and HR using individual (non-averaged) baseline assessments.
- For each of the ECG parameters (HR, and QT, QTc, QRS, PR intervals), descriptive statistics at baseline, at each post-baseline time point and changes from baseline at each post-baseline time point.
- Frequency (number and percentage) of patients with notable ECG values according to the following categories:
 - QTc increase from baseline >30 ms, >60 ms;
 - QTc >450 ms, >480 ms, >500 ms;
 - HR ≤ 50 bpm and decrease from baseline ≥ 20 bpm;
 - HR ≥ 120 bpm and increase from baseline ≥ 20 bpm;
 - PR ≥ 220 ms and increase from baseline ≥ 20 ms;
 - QRS ≥ 120 ms.

Patients with notable ECG interval values and qualitative ECG abnormalities will be listed for each patient and time point and the corresponding notable values and abnormality findings will be included in the listings.

Unscheduled ECG measurements will not be used in computing the descriptive statistics for change from baseline at each post-baseline time point. However, they will be used in the analysis of notable ECG changes and the shift table analysis of notable QT parameters.

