9. Blood Chemistry and Coagulation:	No need to repeat on C1D1 if baseline assessment performed within 7 days prior to that date. On treatment, to be performed prior to dosing with study medications unless otherwise indicated. See Table 10 in Section 7.1.3 , Laboratory Safety Assessments, for the list of the required Laboratory Tests.
10. Urinalysis:	During the treatment period to be performed when clinically indicated. If protein $\geq 2+$ by semiquantitative method (eg, urine dipstick), protein will be quantified by 24 hour urine collection (see Table 10). Urine reflex microscopy is required whenever urine multitest dipstick is positive for blood or protein.
11. Serum/Urine Pregnancy Test (serum/urine):	For female patients of childbearing potential, will be performed on 2 separate occasions prior to starting study treatment: once at the start of screening and once at the baseline visit, immediately before study drug administration.. Following a negative pregnancy result at screening, appropriate contraception must be commenced. Pregnancy tests to be routinely repeated on Day 1 every cycle. Additional pregnancy test to be done whenever one menstrual cycle is missed or when potential pregnancy is suspected. Additional pregnancy tests may also be done if requested by IRB/ECs or if required by local regulations. See Section 4.3 for contraception guidelines.
12. 12-lead ECG:	At each time point, 3 consecutive 12 lead ECGs will be performed approximately 2 minutes apart to determine mean QTc. When coinciding with blood sample draws for PK, ECG assessment should be performed prior to blood sample collection, such that the blood sample is collected at the nominal time. On treatment ECGs will be performed on Day 1 of Cycles 1-4, before and at the end of PF-05082566 infusion and at the end of mogamulizumab infusion. Cycle s>4, ECGs to be performed only if clinically indicated. While pre-dose ECG assessments will be required for all patients, post-dose ECG assessments will be required only for patients in dose-finding cohorts. See Section 7.1.5 for further details.
13. Hepatitis B and C Tests:	Conduct tests for hepatitis B surface antigen, core antibody, and anti-hepatitis C. Other tests may be conducted per standard practice to confirm an active hepatitis infection.

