Pre-dose ECG assessments will be required for all patients, post-dose ECG assessments will be required only for patients in dose-finding cohorts (see [Table 1](#)).

Clinically significant abnormal findings in baseline ECGs will be recorded as medical history.

Clinically significant findings seen on the follow-up ECGs should be recorded as AEs.

When matched with PK sampling, the ECG must be carried out before each PK sample drawing such that the PK sample is collected at the nominal time (ie, the timing of the PK collections over rides the timing of the ECG collections).

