9.1. Analysis sets

1. Full analysis set.

The full analysis set includes all enrolled patients.

2. Safety analysis set.

The safety analysis set includes all enrolled patients who receive at least one dose of study medication.

3. DLT evaluable set.

All enrolled patients who are eligible for the study and receive study treatment. Note that every patient will contribute to the determination of the MTD including patients who are lost to follow-up prior to completion of the 2 cycles' DLT observation period.

4. PK/Immunogenicity and PK parameter analysis sets.

The PK/ADA concentration population is defined as all enrolled patients who have been treated and have at least one post dose concentration measurement of either PF-05082566 or mogamulizumab.

The PK parameter analysis population is defined as all enrolled patients who have been treated and whose concentration-time data allows the estimation of at least 1 of the PK parameters of interest.

5. **CCI**

6. ECG/QTc Analysis set.

Treated patients who have baseline and at least 1 on study ECG/QTc measurement.

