5.2. General Methods

As described in [Section 3.4](#), in this study ‘**treatment group**’ refers to one of the following:

- Dose Level -1: PF-05082566 1.2 mg/kg q4wks + mogamulizumab 0.5 mg/kg;
- Dose Level 1: PF-05082566 1.2 mg/kg q4wks + mogamulizumab 1 mg/kg;
- Dose Level 1a: PF-05082566 100 mg q4wks + mogamulizumab 1 mg/kg;
- Dose Level 2: PF-05082566 2.4 mg/kg q4wks + mogamulizumab 1 mg/kg;
- Dose Level 3: PF-05082566 5 mg/kg q4wks + mogamulizumab 1 mg/kg.

Baseline characteristics, disposition and efficacy data will be summarized based on the FAS by treatment group.

DLTs will be summarized based on the DLT-evaluable set by treatment group.

Other safety data, exposure data, concomitant medications and non-drug treatments will be summarized based on the safety analysis set by treatment group.

PK data will be summarized based on the PK analysis sets by treatment group.

CCI

Immunogenicity data will be summarized based on the immunogenicity analysis set by treatment group.

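### At any dose level also used for expansion, the notable-ECG percentages mix patients with and without scheduled end-of-infusion ECGs, so they understate effects near the end of infusion and cannot be compared with unexpanded levels

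*SAP*

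**What the plan says.** **ECG schedule.** Footnote 12 of the protocol's Schedule of Activities sets the times: "On treatment ECGs will be performed on Day 1 of Cycles 1-4, before and at the end of PF-05082566 infusion", and again at the end of the mogamulizumab infusion. After Cycle 4, ECGs are taken only when clinically indicated. The same footnote then splits the study in two: "While pre-dose ECG assessments will be required for all patients, post-dose ECG assessments will be required only for patients in dose-finding cohorts". Protocol 7.1.5 repeats this. Table 1 adds an ECG at end of treatment.

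**Analysis.** SAP 6.6.7 plans, by treatment group and over the on-treatment period, the number and percentage of patients in each notable category: QTc above 450, 480 or 500 ms, QTc increase above 30 or 60 ms, and criteria for HR, PR and QRS. On the denominator it says: "The denominator to calculate percentages for each category is the number of patients evaluable for the category". Protocol 9.6.2.3 describes the categorical analysis as using each patient's maximum change and maximum post-baseline value across time points.

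**Who is evaluable.** The SAP does not define it for ECGs. The ECG/QTc set in protocol 9.1 is: "Treated patients who have baseline and at least 1 on study ECG/QTc measurement". Neither document asks for a post-dose ECG.

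**Grouping.** SAP 5.2: "Other safety data, exposure data, concomitant medications and non-drug treatments will be summarized based on the safety analysis set by treatment group". The five groups are dose levels, for example "Dose Level 1a: PF-05082566 100 mg q4wks + mogamulizumab 1 mg/kg". None distinguishes dose-finding from expansion, and SAP 6.4 plans no subset analyses.

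**Where expansion can fall.** Protocol 3.4 places expansion at the estimated MTD or lower, and 3.5 allows a 100 mg flat dose, which is Dose Level 1a.

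**The concern.** An any-exceedance percentage depends on how many ECGs a patient has and when they are taken. Following the SAP as written, a patient with ECGs at the end of both infusions and a patient with pre-dose ECGs only count equally in the denominator at the same dose level. An end-of-infusion effect can reach the numerator through a scheduled ECG only in the first kind of patient.

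The expanded level would then tend to show a lower percentage than an unexpanded level with the same true effect, purely because of sampling. At stake is how a descriptive safety table is read. No sample size, hypothesis test or error rate is affected.

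**Working it through.** **1. The plan's own figures.** SAP 5.1.1 gives 30 patients a probability of 0.79 (5% rate) and 0.96 (10% rate) of showing an unexpected toxicity. These reproduce: 1 − 0.95^30 = 0.785 and 1 − 0.90^30 = 0.958. Thirty is also the planned maximum with scheduled post-dose ECGs. The planned total is 30 + 40 = 70, so study-wide up to 40/70 = 57% have none.

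**2. Scheduled ECGs, Cycles 1-4.** The Cycle 1 pre-dose ECG is baseline.

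- Dose-finding: 2 + 3 + 3 + 3 = 11 post-baseline ECGs, of which 2 × 4 = 8 are post-dose.
- Expansion: 0 + 1 + 1 + 1 = 3, all pre-dose.
- Both also have an end-of-treatment ECG about four weeks after the last dose, well away from the end of infusion.

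**3. Share of the denominator without a scheduled post-dose ECG.** Let E be expansion patients at the level and d dose-finding patients there (3 to 9 per cohort, protocol 3.1.9). The share is E/(E + d).

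| E | d = 3 | d = 6 | d = 9 |
|---|---|---|---|
| 5 | 5/8 = 63% | 5/11 = 45% | 5/14 = 36% |
| 10 | 10/13 = 77% | 10/16 = 63% | 10/19 = 53% |
| 20 | 20/23 = 87% | 20/26 = 77% | 20/29 = 69% |
| 40 | 40/43 = 93% | 40/46 = 87% | 40/49 = 82% |

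Levels without expansion patients are at 0%.

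**4. Effect on the percentage.** Suppose an effect appears only at the end of infusion and no unscheduled ECG is taken. The expected pooled percentage is p × d/(d + E), where p is the true rate. For an assumed p = 20% and d = 9:

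- E = 10: 20% × 9/19 = 9.5%
- E = 20: 20% × 9/29 = 6.2%
- E = 40: 20% × 9/49 = 3.7%

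**5. How far pre-dose ECGs are from the peak.** A mono-exponential approximation gives the fraction remaining as 2^(−t/half-life).

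- PF-05082566 at 672 h (28 days): single-agent half-life 135-280 h gives 3-19%; with rituximab, 170-332 h gives 6-25% (protocol 1.2.4.1).
- Mogamulizumab, half-life 184-332 h (protocol 1.2.5.2): before Cycle 2, 168 h after the Day 22 dose, 53-70%; before Cycles 3 and 4, 336 h after the Day 15 dose, 28-50%.

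Pre-dose ECGs are thus far from the PF-05082566 peak but clearly not drug-free, particularly for mogamulizumab.

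**6. What the split does to precision.** With zero events the exact two-sided 95% upper limit is 1 − 0.025^(1/n): 7.3% for n = 49 and 33.6% for n = 9. The pooled figure would suggest precision about post-dose ECGs that the design does not provide.

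**The case against.** **Pooling is inferred.** No sentence says that both portions share a table, expansion might use a dose outside the five groups, and 40 is a ceiling with the final number left to emerging data. This stands as a condition: the problem arises only at a dose level shared by both portions. But the protocol expects shared levels, and dose-only grouping then combines the patients.

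**Other outputs show the post-dose data.** SAP 6.6.7 gives descriptive statistics at each time point and lists notable values by patient and time point. Protocol 9.6.2.3 plans a graphical look at concentration against QTc, and 7.1.5 records clinically significant findings as adverse events. All of this limits the harm. None of it supplies a correct proportion exceeding a threshold.

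**Stronger readings that the documents do not support.**

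- A reader might infer that the table would report only 7-18% of the true rate (3/43 to 9/49). That needs all 40 expansion patients at one level, an effect confined to the end of infusion, and no unscheduled ECGs. The three-patient case also fits poorly with expansion at the MTD, where the stopping rule looks for 9 patients, or 6 with no DLT.
- A reader might infer that a peak effect is invisible in expansion patients. Post-dose ECGs there are not required, but neither are they forbidden. Triplicates are taken at cardiac or neurologic events, and SAP 6.6.7 counts unscheduled ECGs towards notable values. Asymptomatic prolongation could still be missed.
- A reader might infer that the RP2D safety conclusion rests on this table. Protocol 3.3 and 3.6 tie the RP2D to the MTD, DLT data and long-term feasibility. QTc percentages are not a stated criterion, and ECG is not a listed endpoint.
- A reader might want a figure for the extra chance exceedances that 11 rather than 3 ECGs produce. The direction is clear, but the documents give no QTc variability from which to compute it.

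**Conclusion.** The point holds for any dose level used in both portions. There the notable-ECG percentage combines patients with 11 scheduled post-baseline ECGs in Cycles 1-4 and patients with 3, is biased downward for effects near the end of infusion, and is not comparable with unexpanded levels. Between 36% and 93% of the denominator has no scheduled post-dose ECG, depending on whether 5 or 40 expansion patients join 9 or 3 dose-finding patients. The schedule counts assume that patients complete four cycles. The amount of bias also depends on how far the effect is confined to the end of infusion and on how many unscheduled ECGs are taken, neither of which the documents fix. This is worth correcting before the tables are produced, as a matter of interpretation in a descriptive safety display.

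**What to change.** In SAP 6.6.7:

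- Within each dose level, tabulate notable ECG values separately for patients on the post-dose ECG schedule (dose-finding) and on the pre-dose-only schedule (expansion).
- Base any statement about post-dose QTc on the first group alone.
- Show a pooled percentage, if at all, only with a footnote stating that the schedules differ.

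The cost is some SAP wording and one extra table split, with no new data. The post-dose denominators become small: 3 to 9 per dose-finding cohort, so even 0 of 9 leaves an upper limit of 33.6%.
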